5.3.2. Caffeine, Alcohol, and Tobacco

- Participants will be instructed to limit ingesting caffeine- or xanthine-containing products (e.g., coffee, tea, cola drinks, chocolate) for 24 hours prior to the start of dosing until collection of the final pharmacokinetic blood sample.
- Participants will abstain from alcohol for 24 hours prior to the start of dosing until collection of the final pharmacokinetic blood sample.

5.3.3. Activity

- Participants will abstain from strenuous exercise for 24 hours before each blood collection for clinical laboratory tests, for 24 hours prior to admission to the clinical research unit, and while in the clinical research unit. Participants may participate in light recreational activities during studies (e.g., watching television, reading).

5.4. Screen Failures

Screen failures are defined as participants who consent to participate in the clinical study but are not subsequently randomized. A minimal set of screen failure information is required to ensure transparent reporting of screen failure participants to meet the Consolidated Standards of Reporting Trials (CONSORT) publishing requirements and to respond to queries from regulatory authorities. Minimal information includes demography, screen failure details, eligibility criteria, any protocol deviations and any serious adverse events (SAEs).

Individuals who do not meet the criteria for participation in this study (screen failure) may be rescreened participant to consultation with the GSK Medical Monitor. In the case of a re-screen, the participant should be assigned a new participant number.

5.5. Self-isolation

Where it is site policy to do so, participants will be asked to attend the Unit a few days prior to admittance to receive a COVID-19 test (Polymerase chain reaction [PCR] or antigen). Once tested, participants will be asked to self-isolate at home until their admittance to the Unit for their next dosing period.

6. STUDY INTERVENTION

Study intervention is defined as any investigational intervention(s), marketed product(s), placebo, or medical device(s) intended to be administered to a study participant according to the study protocol.

6.1. Study Intervention(s) Administered

Part A

Part A will include a screening visit and 3 treatment periods. These treatment periods, Periods 1, 2 and 3, will be conducted in the same manner; and there will be a minimum of a 7-day washout period between treatment periods. A single dose of investigational product will be administered for each treatment. The screening visit will be conducted within 30 days prior to the first dose in Period 1.

A follow up visit will occur 7 days after administration of the last dose of study medication in Period 3.

- Eligible participants will be enrolled and randomized in a 1:1 ratio to a treatment sequence of either Regimen A, B, or C:

Regimen	Period 1	Period 2	Period 3
A	Daprodustat 4 mg Dissolution profile #1 from Process 2	Daprodustat 4 mg Dissolution profile #2 from Process 2	Daprodustat 4 mg Reference Process 1
B	Daprodustat 4 mg Dissolution profile #2 from Process 2	Daprodustat 4 mg Reference Process 1	Daprodustat 4 mg dissolution profile #1 from Process 2
C	Daprodustat 4 mg Reference Process 1	Daprodustat 4 mg Dissolution profile #1 from Process 2	Daprodustat 4 mg Dissolution profile #2 from Process 2

The total study duration for each participant will be approximately 8 weeks (minimum) for Part A. All participants will receive study treatment according to the randomization schedule.

Part B

For each of the dose strengths being evaluated, the study will be setup and conducted in the same manner, but a different set of healthy volunteers will be recruited. A total of 5 groups of healthy volunteers will be recruited for the respective dose strengths being evaluated. A single dose will be administered for all dose strengths.

Evaluation of each dose strength will include a screening visit and 2 treatment periods; there will be a minimum of a 7-day washout period between study treatment administration in Period 1 and Period 2. The screening visit will be conducted within 30 days prior to the first dose in Period 1 for each dose strength.

There will be a post-treatment follow-up visit 7 days after participants receive last dose of study medication in the second treatment period.

- For the 1 mg dose strength, eligible participants will be enrolled in the study and randomized in a 1:1 ratio to a treatment sequence of either Regimen D or E:

Regimen	Period 1	Period 2
D	Daprodustat 1 mg Process 2	Daprodustat 1 mg Process 1
E	Daprodustat 1 mg Process 1	Daprodustat 1 mg Process 2

- For the 2 mg dose strength, eligible participants will be enrolled in the study and randomized in a 1:1 ratio to a treatment sequence of either Regimen F or G:

Regimen	Period 1	Period 2
F	Daprodustat 2 mg Process 2	Daprodustat 2 mg Process 1
G	Daprodustat 2 mg Process 1	Daprodustat 2 mg Process 2

- For the 4 mg dose strength, eligible participants will be enrolled in the study and randomized in a 1:1 ratio to a treatment sequence of either Regimen H or I:

Regimen	Period 1	Period 2
H	Daprodustat 4 mg Process 2	Daprodustat 4 mg Process 1
I	Daprodustat 4 mg Process 1	Daprodustat 4 mg Process 2

- For the 6 mg dose strength, eligible participants will be enrolled in the study and randomized in a 1:1 ratio to a treatment sequence of either Regimen J or K:

Regimen	Period 1	Period 2
J	Daprodustat 6 mg Process 2	Daprodustat 6 mg Process 1
K	Daprodustat 6 mg Process 1	Daprodustat 6 mg Process 2

- For the 8 mg dose strength, eligible participants will be enrolled in the study and randomized in a 1:1 ratio to a treatment sequence of either Regimen L or M:

Regimen	Period 1	Period 2
L	Daprodustat 8 mg Process 2	Daprodustat 8 mg Process 1
M	Daprodustat 8 mg Process 1	Daprodustat 8 mg Process 2

The total study duration for each participant will be approximately 7 weeks (minimum) for Part B. All participants will receive study treatment according to the randomization schedule.

Daprodustat will be supplied as film coated tablets for oral administration containing 1, 2, 4, 6, or 8 mg of daprodustat. The doses, tablet size, and description are provided in [Table 1](#). Participants are to take the daprodustat tablet(s) daily with water, and these tablets can be taken without regard to food.

Table 1 Description of Daprodustat and Placebo Tablets

Tablet size	Dose	Description
7 mm	Daprodustat 1 mg, 2 mg, 4 mg	7.0 mm round, compound radius, white film coated tablets
9 mm	Daprodustat 6 mg and 8 mg	9.0 mm round, compound radius, white film coated tablets

6.2. Preparation/Handling/Storage/Accountability

The Investigator will be supplied with investigational products in amounts that exceed the quantity needed to perform the clinical trial. Please see the Study Reference Manual for further information.

- The investigator or designee must confirm appropriate temperature conditions have been maintained during transit for all study intervention received and any discrepancies are reported and resolved before use of the study intervention.
 - Only participants enrolled in the study may receive study intervention and only authorized site staff may supply or administer study intervention. All study interventions must be stored in a secure, environmentally controlled, and monitored (manual or automated) area in accordance with the labeled storage conditions with access limited to the investigator and authorized site staff.
 - The investigator, institution, or the head of the medical institution (where applicable) is responsible for study intervention accountability, reconciliation, and record maintenance (i.e., receipt, reconciliation, and final disposition records).

- Further guidance and information for the final disposition of unused study intervention are provided in the Study Reference Manual.
- Under normal conditions of handling and administration, study intervention is not expected to pose significant safety risks to site staff.
- A Material Safety Data Sheet (MSDS)/equivalent document describing occupational hazards and recommended handling precautions either will be provided to the investigator, where this is required by local laws, or is available upon request from GSK.

6.3. Measures to Minimize Bias: Randomization and Blinding

Study using Pre-Coded Randomization provided to site	
On Day (-1), participants will be assigned a unique number (randomization number) in ascending numerical order at each study site(s). The randomization number encodes the participant's assignment to one of the 3 regimen sequences of Part A, or one of the 2 regimen sequences for a given dose strength of Part B in the study, according to the randomization schedule generated prior to the study by the Statistics Department at GSK, or designee. Participants randomized to Part B will only be randomized to one dose strength. Each participant will be dispensed blinded study intervention, labeled with his/her unique randomization number, throughout the study. A central randomization approach will be used.

Blinded study with unblinded site pharmacist who is dispensing drug	
Participants will be randomized in a [1:1] ratio to receive study intervention. Investigators will remain blinded to each participant's assigned study intervention throughout the course of the study. In order to maintain this blind, an otherwise uninvolved 3rd party will be responsible for the dispensation of the study intervention and will endeavor to ensure that there are no differences in time taken to dispense following randomization.
 
Unblinded monitors and in the event of a Quality Assurance audit, the auditor(s) will be allowed access to un-blinded study intervention records at the site(s) to verify that randomization/dispensing has been done accurately.

GSK's Global Clinical Safety and Pharmacovigilance (GCSP) staff may unblind the intervention assignment for any participant with an SAE. If the SAE requires that an expedited regulatory report be sent to one or more regulatory agencies, a copy of the report, identifying the participant's intervention assignment, may be sent to investigators in accordance with local regulations and/or GSK policy.

6.4. Study Intervention Compliance

- When the individual dose for a participant is prepared from a bulk supply, the preparation of the dose will be confirmed by a second member of the study site staff.
- When participants are dosed at the site, they will receive study intervention directly from the investigator or designee, under medical supervision. The date and time of each dose administered in the clinic will be recorded in the source documents. The dose of study intervention and study participant identification will be confirmed at the time of dosing by a member of the study site staff other than the person administering the study intervention. Study site personnel will examine each participant's mouth to ensure that the study intervention was ingested.

6.5. Concomitant Therapy

The Medical Monitor should be contacted if there are any questions regarding concomitant or prior therapy.

Participants must abstain from taking prescription or non-prescription drugs (including vitamins and dietary or herbal supplements) within 7 days (or 14 days if the drug is a potential enzyme inducer, i.e., rifampin/rifampicin, a strong inducer of CYP2C8) or 5 half-lives (whichever is longer) before the start of study intervention until completion of the follow-up visit, unless, in the opinion of the investigator and sponsor, the medication will not interfere with the study.

Because daprodustat is a CYP2C8 substrate, examples of prescription drugs listed below will be prohibited as indicated above (also refer to exclusion criteria Section 5.2):

- Strong inhibitors of CYP2C8 (e.g., gemfibrozil)
- Strong inducers of CYP2C8 (e.g., rifampin/rifampicin)

Paracetamol/Acetaminophen, at doses of \leq 2 grams/day, is permitted for use any time during the study. Other concomitant medication may be considered on a case-by-case basis by the investigator in consultation with the Medical Monitor.

6.6. Dose Modification

No dose modifications will be made during this bioequivalence study.

6.7. Intervention after the End of the Study

Since the study is a pharmacokinetic study in healthy participants, there are no arrangements for post-study treatment of a medical condition.

7. DISCONTINUATION OF STUDY INTERVENTION AND PARTICIPANT DISCONTINUATION/WITHDRAWAL

7.1. Discontinuation of Study Intervention

In rare instances, it may be necessary for a participant to permanently discontinue (definitive discontinuation) study intervention. If study intervention is definitively discontinued, the participant will not remain in the study after his or her discontinuation/early withdrawal assessments. See the SOA for data to be collected at the time of discontinuation of study intervention and follow-up and for any further evaluations that need to be completed.

7.1.1. Liver Chemistry Stopping Criteria

[figure not shown]
Liver chemistry stopping, and increased monitoring criteria have been designed to assure participant safety and evaluate liver event etiology.

Discontinuation of study intervention for abnormal liver tests is required when:

1. a participant meets one of the conditions outlined in the algorithm
2. when in the presence of abnormal liver chemistries not meeting protocol-specified stopping rules, the investigator believes study intervention discontinuation is in the best interest of the participant.

Study intervention will be discontinued **for a participant** if liver chemistry stopping criteria are met:

Phase 1 Liver Chemistry Stopping Criteria – Liver Stopping Event Algorithm

Abbreviations: ALT = alanine transaminase; INR = international normalized ratio; SAE = serious adverse event; ULN = upper limit of normal.

Refer to [Appendix 5](#) for required Liver Safety Actions and Follow up Assessments

7.1.2. Other Stopping Criteria

A participant must permanently stop dosing for the pre-specified reasons below.

- Hemoglobin actual value >1 g/dL over 2 weeks following dosing
- Becomes pregnant
- Diagnosis of cancer (new or recurrent), with the exception of localized squamous cell or basal cell carcinoma of the skin
- Need for more than 14 days use of prohibited medication (Section [6.5.](#))

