1.3. Schedule of Activities (SoA)

Part A -OR- Part B

Procedure	Screen ¹	Intervention (Part A Periods 1, 2, & 3 OR Part B Periods 1 & 2) ¹⁰												Follow-up ⁹
		Day -1	Pre-dose	0h	0.5h	1h	2h	2.5h	3h	4h	6h	8h	12h	
Informed Consent	X													
Inclusion / Exclusion ²	X	X												
Demography	X													
Physical Examination ³	X	X												
12-Lead electrocardiogram (ECG)	X													
Vital Signs ⁴	X	X	X											X
Clinical Laboratory Test ⁵	X	X												X
Pregnancy Test ⁶	X	X												X
Urine Drug Screen and Alcohol Screen ⁷	X													
Randomization		X												
Study Intervention Dose ⁸				X										
PK Blood Sampling			X		X	X	X	X	X	X	X	X	X	
AE/Serious AE		←-----→												
Concomitant Medication Review		←-----→												
Admission to Unit		X												
Discharge from Unit														X
Outpatient Visit	X													X
COVID-19 testing (PCR or antigen)	X	X ¹²		<-----Ad hoc based on continuous review----->										

¹Within 30 days of Day 1, Period 1

²Re-check eligibility at Day -1 (admission to Unit)

³Brief Physical Examination on Day -1

⁴Body temperature, pulse, systolic & diastolic blood pressure (semi-supine)

⁵ Hematology, clinical chemistry (including liver), and urinalysis

⁶ Urine or serum per site standard; females only

⁷ Alcohol screening can be performed via urine or breathalyser per site standard

⁸ Time 0 is the time of study interventional drug dosing, and all subsequent timed assessments are calculated from Time 0.

⁹ 7 (± 1) days from dose day Period 3, Part A -OR- 7 (± 1) days from dose day Period 2, Part B. Same assessments will be performed for early withdraw visit.

¹⁰ A minimum of 7 days is required between each treatment-period's dosing, i.e., at least 7 days between Period 1 and Period 2, and between Period 2 and Period 3 dosing in Part A, and 7 days between Period 1 and Period 2 dosing in Part B

¹² COVID-19 PCR or antigen testing may be done prior to Day -1 (admission to the study unit) such that the results are timed to arrive just prior to admission, ideally within 72h of admission to the study unit.

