7.1.3. Temporary Discontinuation

There is no provision in this relative and bioequivalence study for a temporary discontinuation per se. Withdrawal from study intervention (i.e., the decision of either the participant or the Principal Investigator to stop dosing or not complete all dosing occasions) will require the participant's withdrawal from the study (see Section [7.2](#)).

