8. STUDY ASSESSMENTS AND PROCEDURES

- Study procedures and their timing are summarized in the SoA.
- Protocol waivers or exemptions are not allowed
- Immediate safety concerns should be discussed with the sponsor immediately upon occurrence or awareness to determine if the participant should continue or discontinue study intervention.
- Adherence to the study design requirements, including those specified in the SoA, is essential and required for study conduct.
- All screening evaluations must be completed and reviewed to confirm that potential participants meet all eligibility criteria. The investigator will maintain a screening log to record details of all participants screened and to confirm eligibility or record reasons for screening failure, as applicable.
- Procedures conducted as part of the participant's routine clinical management (e.g., blood count) and obtained before signing of ICF may be utilized for screening or

baseline purposes provided the procedure met the protocol-specified criteria and was performed within the time frame defined in the SoA.

- The maximum amount of blood collected from each participant over the duration of the study, including any extra assessments that may be required, will not exceed 500 mL.
- Repeat or unscheduled samples may be taken for safety reasons or for technical issues with the samples.

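### The hemoglobin stopping rule in Protocol 7.1.2 sets a limit that every healthy adult exceeds; it should be a rise from a named baseline

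*Protocol*

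**What the plan says.** Protocol 7.1.2 opens with "A participant must permanently stop dosing for the pre-specified reasons below", and the first reason listed is "Hemoglobin actual value >1 g/dL over 2 weeks following dosing". The bullet does not mention an increase, a change or a reference value.

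The surrounding text fixes the force of the rule:

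- Protocol 7.1: "If study intervention is definitively discontinued, the participant will not remain in the study after his or her discontinuation/early withdrawal assessments".
- Protocol 7.1.3: a decision to stop dosing "will require the participant's withdrawal from the study".
- Protocol 8: "Protocol waivers or exemptions are not allowed".
- Protocol 7.1 also sets the expected frequency: "In rare instances, it may be necessary for a participant to permanently discontinue" study intervention.

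In the Schedule of Activities (Protocol 1.3), clinical laboratory tests are marked at screening, Day -1 and follow-up. The footnote defines them as "Hematology, clinical chemistry (including liver), and urinalysis". The Day -1 column sits under a heading that covers "Part A Periods 1, 2, & 3 OR Part B Periods 1 & 2". Another footnote requires at least 7 days between doses.

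The SAP (4.1.1, baseline definition) takes the latest non-missing pre-dose value as baseline. Its table gives Day -1 as the baseline used in hematology displays. It does not refer to the stopping rule.

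**The concern.** A stopping limit has to separate the people it is meant to protect from everyone else, and this one cannot. Protocol 2.3 names thrombosis with ischemia secondary to erythrocytosis as a primary area of interest, and this bullet is the only stopping criterion with a hemoglobin threshold. The eligibility criteria set no hemoglobin limit either.

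A site therefore cannot apply the rule as worded and has to supply its own version. Even if every site reads it as a rise, the comparator is left open: screening, Day -1 of Period 1, or Day -1 of the current period. With doses as little as 7 days apart, a 2-week window can contain more than one dose, so the choice can change who is stopped. Any sensible application also departs from the literal text of a protocol that allows no waivers.

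**Working it through.** The documents derive no figure from this rule, so there is none to reproduce. The check has four parts.

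**1. Does the limit discriminate?** With hemoglobin taken as normal with mean m and SD s (assumed), P(Hgb > 1) = 1 - Phi((1 - m)/s). Even at m = 8 and s = 2 g/dL, far below a healthy population, this is 1 - Phi(-3.5) = 0.9998. At m = 12 or more with the same SD it is 1 to seven decimals. The limit carries no information in healthy volunteers.

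**2. What was meant?**

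- Protocol 2.2 says the drug increases erythropoiesis and raises hemoglobin.
- Protocol 2.3 names erythrocytosis as the hazard.
- Protocol 7.1 expects permanent discontinuation only rarely.
- A period of 2 weeks fits a change better than a level.

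Together these point to a rise of more than 1 g/dL within 2 weeks of dosing. This is an inference; neither document states it.

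**3. Does the comparator matter?** Take two successive between-period rises of size a, with 0.5 < a < 1 g/dL. Against Period 1 Day -1 the total is 2a > 1, so the participant stops. Against each period's own Day -1 every rise is below 1, so the participant continues. A baseline reset each period can therefore hide a cumulative rise.

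The fixed baseline has a limit of its own. With d days between doses, Period 1 Day -1 and Period 3 Day -1 are 2d days apart: 14 at d = 7, 20 at d = 10, 28 at d = 14. It matches a 2-week window only at the minimum spacing.

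**4. What would a rise rule cost in noise stops?** Assume no true change and independent normal errors with within-person SD s. Neither document gives s; 0.3 to 0.6 g/dL is assumed.

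- One pair of measurements: P = 1 - Phi(1/(s√2)).
- Part A, two later checks against one fixed baseline: P = 1 - ∫ Phi(z + 1/s)² φ(z) dz.

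| s (g/dL) | One pair | Part B, × 210 randomized | Part A, two checks | Part A, × 36 randomized |
|---|---|---|---|---|
| 0.3 | 0.92% | 1.9 | 1.7% | 0.6 |
| 0.45 | 5.8% | 12.2 | 10.1% | 3.6 |
| 0.6 | 11.9% | 25.1 | 19.7% | 7.1 |

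The planned margins (Protocol 5) are 210 - 190 = 20 in Part B and 36 - 30 = 6 in Part A. Noise alone would equal them at s of about 0.54 (20/210 = 9.5%) and 0.55 (6/36 = 16.7%).

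The counts also assume that Day -1 laboratory tests are repeated in every period. The column heading supports that but does not prove it, because the same column holds randomization, which happens once. The range is too wide to say whether the margins would hold. It shows only that a 1 g/dL rise rule has a cost that the clinical team should weigh.

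**The case against.** A reader might infer that, as written, every participant must stop after the first dose and no crossover can be completed. The documents do not support that as an expected consequence, because it depends on one parsing of the bullet. Read as a value that persists over 2 weeks, the rule could not be judged met before Day 15. At the 7-day minimum, Part B's second and last dose falls on Day 8. Read as a rate of change, nobody stops for having a normal hemoglobin. The expectation that discontinuation is rare favors the rise reading, and sites would probably adopt it. This part of the objection stands: the harm to expect is inconsistent application.

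It is also fair to say that the baseline gap is narrower than it first looks, since the SAP's hematology row already names Day -1. That table governs data displays rather than site decisions, and it leaves open which period's Day -1 would apply to a stopping rule.

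The noise figures rest on an SD that is in neither document, and they describe the cost of the repaired rule, not the size of the defect. They also ignore drift; repeated blood sampling would, if anything, lower hemoglobin and reduce false stops. That stands, and the figures should be read only as a range.

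Finally, the practical risk is small. Protocol 2.3 reports no clinically significant safety findings at single doses up to 500 mg in healthy subjects, against 1 to 8 mg here. Investigator withdrawal, laboratory review and sponsor contact all remain. That limits the severity but does not make the threshold right.

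**Conclusion.** The criterion is wrong as written and should be corrected. It is a drafting error in a mandatory safety rule: current, complete text, with nothing elsewhere in either document that rewords it or gives it a comparator. That an actual value above 1 g/dL does not discriminate needs no assumption beyond the participants being healthy. That a rise was meant is a well-supported inference.

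The likely consequence is that sites apply different comparators to the same rule. The documents give no data on how many participants would show a true rise above 1 g/dL, so the number of decisions affected cannot be stated. Sample size, power and the bioequivalence analysis do not change.

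**What to change.** Reword the bullet in Protocol 7.1.2 as an increase in hemoglobin of more than 1 g/dL from the pre-dose Day -1 baseline within 2 weeks following dosing, and state which period's Day -1 is meant. This agrees with the Day -1 hematology baseline in the SAP. Period 1 Day -1 is a sensible default because it does not hide a cumulative rise, but the documents do not require it. The clinical team should confirm the threshold, the baseline, and the window to use when doses are more than 7 days apart.

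Add that the Day -1 hemoglobin is reviewed before each later dose. A rise first seen at the follow-up visit leads to safety follow-up only, since no dose remains to be withheld.

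The cost is a short amendment. If Day -1 laboratory tests recur each period, as the schedule's column heading indicates, no visit or blood draw is added. The downside is the noise stops worked out above. They come with any rule based on a rise of more than 1 g/dL, and Protocol 9.2 already permits replacement of withdrawn participants.
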